Protocol Title: Early Fortification of Human Milk for Very Low Birth Weight Infants and Effects on Growth Velocity

Principal Investigator: [name], DO

1. Objectives

Describe the purpose, specific aims, and hypothesis:

The purpose of this investigation is to determine whether early fortification of human milk feeds improve growth outcomes for very low birth weight infants (VLBW) (birth weight 1000-1500 grams). We hypothesize that introducing higher caloric feeds at the onset of enteral feeds will improve early growth metrics in VLBW infants as compared to infants who begin human milk fortification after the first week of life, which represents our present standard of care. The primary outcome for this study is growth velocity (g/kg/day) at 28 days of life.

2. Background

Describe the background and rationale for the study:

Human milk, maternal or donor milk, is the standard of care for feeding premature infants. However, human milk alone does not provide sufficient energy, protein, fat, and micronutrients to meet the demands of the VLBW premature infant. Thus, slow growth can persist for preterm infants and catch-up growth can be incomplete even after discharge from the NICU, and slow extra-uterine growth (weight, length, and head circumference) is associated with poor neurodevelopment and lower intelligence in school age children born preterm. Using human milk fortifiers (HMF) increase nutrient density of human milk and allows for infants to maintain a human milk-based diet, which has been shown to reduce the incidence of necrotizing enterocolitis (NEC) and improve cognitive outcomes in preterm infants.

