Fortification of human milk is institution-specific and no standard of care has been recommended regarding the timing of fortification of human milk feeds in preterm infants. Much of the concern for earlier fortification arise over whether comorbidities, such as NEC and feeding intolerance, will be more prominent in infants provided early fortification versus delayed fortification. To date, no studies have demonstrated a relationship between human milk fortifiers and the incidence of NEC or feeding tolerance. Thus, delays in introducing HMF may represent an unwarranted safety concern that interferes with supplying an appropriate nutrient-enriched diet to preterm infants. For example, 34.3% of preterm infants are diagnosed with post-natal growth failure at the Children's Hospital of Georgia. Further, later introduction of HMFs may lead to longer time to reach full enteral feeds, total duration on total parenteral nutrition (TPN), or duration of central venous line use. Current available evidence suggests that fortification of human milk starting at the first feed is safe and well-tolerated and may have substantial benefit for preterm infant growth.

3. Inclusion and Exclusion Criteria

List the inclusion/exclusion criteria:

Inclusion:

1. Birth weight 1000-1500 grams
2. Admitted to AU NICU within 24 hours of life
3. Maternal intent to use human milk (maternal or donor milk)

Exclusion:

1. Congenital anomalies including congenital heart disease or other major defect requiring surgical intervention
2. Feeds not started within first 96 hours of life
3. Intrauterine growth restriction (IUGR) defined as <3rd % on a gender specific Fenton growth curve

4. Number of Subjects/Records/Samples Collected

Indicate the total number of subjects to be accrued/records reviewed/samples collected across all sites:

The sample size was determined assuming an alpha level of 0.05, power of 80%, a common standard deviation of 3.64, and a two-sided two-sample t-test to examine differences in weight growth velocity at 28days between the two feeding protocol groups. The mean for the standard of care group (fortification beginning on day 8) was 10.6% and for the intervention group (fortification beginning on day 1) was 12.3, 12.6 and 13.6. The sample size required for each mean difference is below

Assumed Mean in Each Group		Sample Size 2. per Group
Fortification Day 8	Fortification Day 1	
10.56	12.25	74
10.56	12.56	53
10.56	13.56	25

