Briefly describe the actual source records or measures that will be used to collect data about participants. (All surveys, interview scripts, and data collection forms will be attached elsewhere in the application. Do not add other documents to the protocol.) Describe what data will be collected and how it will be collected at all measurement/data collection time-points.

Data will be collected from the patient's EMR. Data to be collected include: date of birth, gender, estimated gestation age (EGA), Apgar score at 1 and 5 minutes, weights, head circumference, length, z-scores for weight, length, and head circumference, total volume of feeds and TPN, number of missed enteral feeds, maternal milk vs donor milk volumes. Laboratory data including basic metabolic panel, magnesium, phosphorus, alkaline phosphatase and urine sodium, potassium and magnesium will be collected on day 22 as per the current standard of care. No blood collections or other procedures will be performed specifically for the study. Clinical outcomes will be collected to include: incidence of metabolic acidosis, NEC, oxygen requirement at 36 weeks, PDA, and death.

Anthropometrics

Anthropometrics are measured as part of the standard physical assessment of the preterm infant. For this study, all anthropometric measurements and calculations will follow AU's standard preterm infant physical assessment guidelines.

Weight

1. Body weight will be measured within 24 hours of birth and then every 7 days until 28 days of life and again at 36 weeks post-menstrual age (PMA).
2. Measurement of weight will be performed by the principal investigator (PI) and/or co-Investigators
3. Weight will be measured (x 2) on a tared infant scale calibrated to the nearest 10 grams. Weights will be recorded in grams (g). Discrepancies of greater than 20g will be repeated.
4. Infants will be weighed without a diaper.
5. Average weight will be recorded in the EMR and documented in the database.
6. Weight will be plotted on a gender-specific Fenton growth chart in the EMR and the percentile recorded in the database

Weight Gain

1. Weight gain and growth velocity (GV) will be calculated at 28 days of life and 36 weeks PMA.
2. Weight gain will be recorded as g/day
3. GV will be calculated as follows and recorded in the database:

$$GV \text{ (g/kg/day)} = \frac{[1000 \times (Wn - W1)]}{(Dn - D1) \times \left[\frac{Wn + W1}{2} \right]}$$

W= weight in grams

D = day

1 = interval of time chosen

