- e. Milk collection labels with a unique bar-code generated by the Cerner Bridge® bar-code system

2. All breastmilk will be processed and prepared in the NICU Milk Lab by trained technicians per standard policy and procedure.
3. The Cerner® Bridge label on each container of breastmilk will be scanned and recorded into the Cerner® Bridge breastmilk management system.
4. All containers of mother's milk collected in one 24 hour span of time will be pooled into a single container per standard NICU Milk Lab procedure. Expiration date and times will be adjusted by Cerner® Bridge once each container is scanned and combined.

2. *Describe the procedures performed to lessen the probability or magnitude of risks:*

As the only intervention that deviates from current standard of care is the use of HMF from feeding day 1 to feeding day 7, we do not anticipate any unique risks for study participants in either group. All SOPs for the handling of human milk and bedside feeding will be followed.

3. *Describe the duration of an individual subject's participation in the study and the time involved also include the overall duration of the project:*

Neonates will be enrolled in the study from birth until 36 weeks post-menstrual age or discharge from the NICU, whichever comes first. Estimated time in the study is two to twelve weeks depending on gestational age at birth.

9. Data and Specimen Management

a. Describe the data analysis plan, including any statistical procedures:

All statistical analysis will be performed using SAS 9.4 and statistical significance will be assessed using an alpha level of 0.05. Descriptive statistics within fortification group (day 1 or day 8) will be determined including means and standard deviations for continuous variables, frequencies and percentages for categorical variables, and medians and interquartile ranges for ordinal variables. Distributional assumptions will be examined before testing and if violations to the assumptions occur a transformation or nonparametric methods will be used. Missing data will not be imputed.

N/A

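### Study participation can end before the day-28 weight that the primary outcome needs, and the accrual target of 50 keeps the stated 80% power only if at most one infant lacks that weight

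*Protocol*

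**What the plan says.** Protocol section 1 fixes the endpoint: "The primary outcome for this study is growth velocity (g/kg/day) at 28 days of life". In section 8, under Weight, infants are weighed within a day of birth, "then every 7 days until 28 days of life and again at 36 weeks post-menstrual age (PMA"). Under Weight Gain: "Weight gain and growth velocity (GV) will be calculated at 28 days of life and 36 weeks PMA". Neither place makes an exception for any infant.

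Section 8, item 3 (duration), says: "Neonates will be enrolled in the study from birth until 36 weeks post-menstrual age or discharge from the NICU, whichever comes first". It adds: "Estimated time in the study is two to twelve weeks depending on gestational age at birth".

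Section 3 selects on birth weight, 1000 to 1500 g, and lists no gestational age limit. The one criterion that restricts maturity indirectly is an exclusion: "Intrauterine growth restriction (IUGR) defined as <3rd % on a gender specific Fenton growth curve".

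Sections 4 and 9b give 25 per group, 50 in all, for a difference of 3.00 g/kg/day (10.56 against 13.56) with SD 3.64, two-sided alpha 0.05 and 80% power. Section 4 answers a question about how many subjects will be accrued, so 50 is an enrolment number. Section 9a states: "Missing data will not be imputed".

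**The concern.** The weighing schedule takes for granted that day 28 comes before 36 weeks PMA. For an infant born late enough the order is reversed. The schedule then calls for a primary-outcome weight after the duration rule has ended that infant's participation. Two members of the same team could include or exclude that infant's primary outcome and each be following the protocol. Because nothing is imputed, an excluded infant drops out of the primary t-test.

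This matters more because the sample size is the smallest that reaches 80% with complete data. The 36-week rule is one of several routes to a missing day-28 weight. The others are discharge before day 28, the withdrawal criteria in section 11a, and death, which is among the outcomes listed in section 8: "Clinical outcomes will be collected to include: incidence of metabolic acidosis, NEC, oxygen requirement at 36 weeks, PDA, and death".

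**Working it through.** **Step 1: when the duration rule falls before day 28.**

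Inputs: the 36-week end point (section 8, item 3) and the day-28 outcome (section 1). 36 weeks is 36 × 7 = 252 days, so days from birth to 36 weeks PMA = 252 − gestational age at birth in days. Counting birth as day 0:

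| Gestational age at birth | Days to 36 weeks PMA | Day 28 reached first? |
|---|---|---|
| 24w0d (168 d) | 84 (12 weeks) | yes |
| 32w0d (224 d) | 28 | same day |
| 32w1d (225 d) | 27 | no |
| 33w0d (231 d) | 21 | no |
| 34w0d (238 d) | 14 (2 weeks) | no |

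Any birth after 32w0d is affected. Counting birth as day 1 moves the boundary by a single day and changes nothing of substance.

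The protocol's own estimate of time in the study starts at two weeks, which is half of the 28 days needed. Under the 36-week rule alone, two to twelve weeks would correspond to births from 34w0d to 24w0d.

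**Step 2: reproduce the sample size.**

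Inputs (sections 4 and 9b): SD 3.64, two-sided alpha 0.05, power 80%, equal groups, two-sample t-test. Power comes from the noncentral t distribution with n1 + n2 − 2 degrees of freedom and noncentrality δ / [SD × √(1/n1 + 1/n2)].

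| Difference | Smallest n per group reaching 80% | Protocol |
|---|---|---|
| 12.25 − 10.56 = 1.69 | 74 | 74 |
| 12.56 − 10.56 = 2.00 | 53 | 53 |
| 13.56 − 10.56 = 3.00 | 25 | 25 |

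All three rows agree with no inflation, so 25 is a number of evaluable infants.

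**Step 3: power for 3.0 g/kg/day when some infants lack the outcome.**

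For 25 v 25 the noncentrality is 3 / (3.64 × √(2/25)) = 2.914 on 48 degrees of freedom, which gives 81.5%. In the same way:

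| Evaluable | Power |
|---|---|
| 25 v 25 (50) | 81.5% |
| 25 v 24 (49) | 80.6% |
| 24 v 24 (48) | 79.8% |
| 22.5 per group (assumed 10% loss) | 77.1% |
| 20 per group (assumed 20% loss) | 71.9% |

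If both losses fall in one arm (25 v 23), power is 79.7%, so the conclusion for 48 does not depend on how they split. The protocol gives no loss rate. The last two rows are illustrations, not forecasts.

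**The case against.** The best reply is that the conflict is narrow and may cost nothing. It concerns only infants born after 32w0d who weigh no more than 1500 g, are not below the 3rd percentile, and are still in the NICU at day 28. Section 8 says that data come from the medical record and that anthropometrics are routine, so a day-28 weight may exist anyway. The duration statement answers a template question and does not forbid use of that weight. The study is at one centre, so one team is reading its own protocol. As for power, going from 81.5% to 79.8% is immaterial, and a missing attrition allowance is not an arithmetical error.

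Much of this stands. The number affected may well be small, the sample size arithmetic is right, and losing two infants hardly changes power. But section 8 has investigators take the study weight in duplicate, which an ordinary charted weight need not match, and no text settles which rule prevails.

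Four stronger readings are tempting, and the protocol does not support them:

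- A reader might infer that the two-week figure proves the 36-week rule will remove infants. It is labelled an estimate and follows a sentence that also ends participation at discharge, so early discharge may explain it. It shows only that follow-up shorter than 28 days is expected.
- A reader might infer that the design tolerates no loss at all. It tolerates one.
- A reader might take the ticked not-applicable box at section 11c to mean that data collection stops at withdrawal. Such marks also sit beside completed sections (12a, for example), so the box is not reliable evidence.
- A reader might infer bias between arms from the 36-week rule. Gestational age at birth is fixed before randomisation, so that rule does not itself favour an arm. Discharge comes after randomisation and could be related to growth, but the protocol gives nothing from which to judge that.

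**Conclusion.** The point holds as an inconsistency between the duration rule and the endpoint schedule, with a related weakness in the stated power. Births after 32w0d reach the end of participation before the primary outcome is due, and the protocol does not say which rule prevails. If the duration rule is applied, obtainable primary outcomes are discarded. The consequence is lost precision and a narrower analysed population, of a size that the document does not let one calculate.

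The claim of 80% power is true only if at least 49 of the 50 infants have a day-28 weight. That statement rests on the protocol's own SD and difference. The figures of 77.1% and 71.9% rest in addition on assumed losses of 10% and 20%. This should be fixed because it touches the only powered outcome and is cheap to correct. It does not undermine the trial.

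**What to change.** Amend section 8, item 3, so that data collection for an infant still in hospital continues to the later of 28 days of life and 36 weeks PMA. Say that the day-28 weight already scheduled under Weight enters the primary analysis for these infants. In sections 4 and 9b, state the power for the number of infants expected to have a day-28 weight, giving the expected loss as an explicit assumption.

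The cost is a short amendment, a few extra duplicate weights in hospital, and a slightly lower stated power. The change recovers only the infants lost through the 36-week rule. Those discharged before day 28 would still lack the outcome, and withdrawals and deaths still count against the evaluable number, so the restated power should allow for them.

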A sample size of 25 per group, for a total of 50 subjects will be needed.

5. Recruitment Methods

Describe when, where, and how potential subjects will be recruited:

All neonates admitted to the NICU who have a birth weight of 1000-1500 grams will be eligible for this study. Screening will include chart review to ensure inclusion criteria is met. Parents (legal guardians) of eligible neonates will be approached for study participation by the PI or co-Investigators.

6. Multiple Site	 N/A
7. Reliance Agreements/Single IRB	 N/A

8. Procedures Involved

a. Describe the procedures involved to include those procedures that are standard evaluation and/or care and those that are solely for research purposes:

Feeding Protocol

All VLBW infants in AU's NICU are provided a standard feeding protocol that has been in use since 2011 and includes fortification of human milk with Enfamil High Protein Liquid Human Milk Fortifier (HP HMF) on feeding day 8. Study participants will be randomly assigned to receive standard of care (ie fortification on feeding day 8) or fortification on feeding day 1. In general, feedings for preterm infants are started in the first 48 hours.

b. Describe and explain the study design:

If the study involves multiple conditions where each condition involves different procedures, please provide a table that breaks down the procedures by condition and in chronological order. Include when and where they are performed.

1. Subjects will be randomly assigned to one of two groups using blocked randomization to ensure equal allocation throughout enrollment. Blocks of size 4 and 6 will be randomly determined and then the group assignment will be randomly permuted within each block. Initiation of enteral feedings, enteral volume advancement, and weaning off parental nutrition will follow the standardized NICU feeding protocol.
2. Subjects will be fed a diet of human milk per standard NICU feeding protocol. Should maternal milk supply be inadequate to meet daily volume needs, donor milk will be used per standard NICU feeding protocol. Importantly, mothers (or guardians) must provide written consent for donor human milk. This consent is separate from the study consent and will be required for study participation.
3. Enfamil High Protein Liquid Human Milk Fortifier (HP HMF) will be used to fortify maternal milk.

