To examine differences between the two groups and assess for potential confounding variables two-sample t-tests will be used for continuous variables, chi-square tests will be used for categorical variables, and Wilcoxon Rank Sum tests will be used for ordinal data. Variables that will be examined include all collected EMR data (e.g., demographics, feeding related, laboratory, and clinical measures) and anthropometric measures.

To examine differences between the two groups (day 1 vs. day 8), a simple two-sided two-sample t-test will be used as a preliminary test for differences in continuous outcomes (e.g., weight growth velocity, head circumference growth velocity, length growth velocity, zscores). Then, to control for various potential confounders or covariates, analysis of covariance (ANCOVA) will be used with the main effect of interest being the group effect. Covariates that will be adjusted for include gestational age, total number of feed interruptions, incidence of metabolic acidosis, and NEC. Because there are only two groups, no adjustment to the overall alpha level will be needed to control for multiple comparisons.

b. When applicable, provide a power analysis:

N/A

The sample size was determined assuming an alpha level of 0.05, power of 80%, a common standard deviation of 3.64, and a two-sided two-sample t-test to examine differences in weight growth velocity at 28days between the two feeding protocol groups. The mean for the standard of care group (fortification beginning on day 8) was 10.6% and for the intervention group (fortification beginning on day 1) was 12.3, 12.6 and 13.6. The sample size required for each mean difference is below

Assumed Mean in Each Group		Sample Size per Group
Fortification Day 8	Fortification Day 1	
10.56	12.25	74
10.56	12.56	53
10.56	13.56	25

A sample size of 25 per group, for a total of 50 subjects will be needed.

c. Describe how data and specimens will be handled:
 
Data will be collected and recorded on a coded spreadsheet that is stored on a research specific Box drive assigned by AU IRB.
	 N/A

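### Post-randomisation variables are tested between arms as possible confounders, and the open ANCOVA list already names three of them, so the adjusted group effect can lose part of the treatment effect

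*Protocol*

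**What the plan says.** All of the analysis text is in Section 9a of the protocol.

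- **Purpose of the first set of tests:** "To examine differences between the two groups and assess for potential confounding variables two-sample t-tests will be used for continuous variables". Chi-square tests are named for categorical variables and Wilcoxon rank sum tests for ordinal ones.
- **Scope of those tests:** "Variables that will be examined include all collected EMR data (e.g., demographics, feeding related, laboratory, and clinical measures) and anthropometric measures". Nothing restricts this to baseline.
- **Adjusted analysis:** continuous outcomes are first compared by a t-test described as preliminary. Then, "to control for various potential confounders or covariates, analysis of covariance (ANCOVA) will be used". The covariates are said to include gestational age, number of feed interruptions, metabolic acidosis and NEC.

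Section 8 (Data Types and Source Records) shows what the EMR set holds: feed and TPN volumes, missed enteral feeds, maternal and donor milk volumes, metabolic acidosis, NEC, oxygen requirement at 36 weeks, PDA and death. Of the laboratory panel it says that it "will be collected on day 22 as per the current standard of care". The anthropometric measures include the weights from which the primary outcome is calculated.

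On allocation, Section 8b says: "Subjects will be randomly assigned to one of two groups using blocked randomization to ensure equal allocation throughout enrollment".

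**The concern.** Confounding of a treatment comparison needs a common cause of treatment and outcome. Random allocation removes it, so a baseline difference between the arms is chance and its p-value says nothing about whether adjustment is needed. That decision should rest on how strongly the variable predicts growth.

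A difference that arises after randomisation is a possible effect of treatment. The protocol itself expects such effects. Section 2 suggests that later fortification may prolong the time to full feeds and the time on TPN. Section 8 (Blinding Procedures) treats feeding tolerance as an important secondary outcome. Section 12 lists a possible increase in NEC risk. Section 9a nevertheless places these kinds of variable among the candidates for confounding.

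At stake is the adjusted group effect. Because the t-test is called preliminary, the ANCOVA reads as the analysis on which the conclusion will rest. If it holds constant something through which early fortification acts, it no longer estimates the whole effect of the feeding policy.

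**Working it through.** **1. The plan's own figure.** Section 9b gives: "The sample size was determined assuming an alpha level of 0.05, power of 80%, a common standard deviation of 3.64". It continues "The mean for the standard of care group (fortification beginning on day 8) was 10.6" (10.56 in the table) and "for the intervention group (fortification beginning on day 1) was 12.3, 12.6 and 13.6" (12.25, 12.56 and 13.56 in the table). The differences are 1.69, 2.00 and 3.00.

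Normal approximation: n per group = 2 × (1.960 + 0.842)² × 3.64² / d².

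| d | Formula, rounded up | Noncentral t | Protocol |
|---|---|---|---|
| 1.69 | 72.8 → 73 | 74 | 74 |
| 2.00 | 52.0 → 52 | 53 | 53 |
| 3.00 | 23.1 → 24 | 25 | 25 |

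The protocol's figures are reproduced exactly by the t-based calculation. Power at 25 per group and a difference of 3.00 is 81.5%. The calculation is for the unadjusted t-test, so changing the covariate list does not alter it.

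**2. Timing of the four named covariates.**

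| Covariate | Timing |
|---|---|
| Gestational age | Baseline |
| Number of feed interruptions | After feeding starts |
| Metabolic acidosis | Listed in Section 8 as a clinical outcome |
| NEC | Listed in Section 8 as a clinical outcome; Section 12 allows that treatment may raise its risk |

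Three of the four can be affected by allocation.

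**3. What adjusting for a mediator does.** Let the total effect be T and let the post-randomisation variable carry a share s of it. In a linear model with no unmeasured common cause of that variable and growth, the ANCOVA group coefficient estimates T × (1 − s). With T = 3.0, the difference behind the chosen sample size:

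- s = 0: 3.0 × 1.00 = 3.0
- s = 0.25: 3.0 × 0.75 = 2.25
- s = 0.50: 3.0 × 0.50 = 1.5

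A simulation of 20,000 trials (25 per arm, SD 3.64) gave about 3.0, 2.25 and 1.50. The shares are assumptions; the protocol has no mediation data.

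**4. If entry depended on a significant between-arm test.** This rule is assumed, not stated in the protocol. A variable that treatment shifts by 0.5 SD is flagged at p < 0.05 in about 41% of trials, and one shifted by 0.8 SD in about 79%. Averaged over trials that adjust only when the variable is flagged:

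| Share mediated | Shift 0.5 SD | Shift 0.8 SD |
|---|---|---|
| 25% | 2.53 | 2.33 |
| 50% | 2.06 | 1.67 |

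**5. If every screened variable were unaffected by treatment.** With 28 null variables (an approximate count from Section 8), four of them prognostic, and the same assumed entry rule, the group estimate was unbiased. The type I error was 3.9%, 5.0%, 5.4% and 3.4% at pairwise correlations of 0, 0.3, 0.5 and 0.8. The harm therefore comes from covariates that treatment affects, not from chance flags.

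**The case against.** The strongest reply is that nothing in the protocol joins the tests to the model. No entry rule is given, and four covariates are named without reference to any test result. This stands. The link is an inference from the shared language of potential confounders and from a list that is introduced but not closed. It does not remove the point, because three of the four named covariates already have the problem without any screening.

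A second reply is that the tests have two purposes, the first being simply to compare the arms. This also stands, and it limits the remedy. The sentence holds the plan's only stated chi-square and Wilcoxon tests, and the ANCOVA paragraph covers only continuous outcomes. Deleting it would leave NEC, PDA, death and acidosis without a stated comparison.

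A third reply is that the unadjusted t-test, on which the sample size rests, is untouched. That is correct.

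Two stronger readings are tempting. A reader might infer that testing many variables at 0.05 inflates the false-positive rate of the primary comparison. The chance of some flag among many null variables is indeed high, but it measures neither bias nor type I error, and step 5 shows the error staying near or below 5%. A reader might also infer that the outcome weights will enter as covariates. They are among the variables tested, but no sentence puts them in the model.

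**Conclusion.** The point holds in limited form. Section 9a gives between-arm tests a purpose they cannot serve in a randomised trial, applies them to variables that treatment may change, and follows them with an ANCOVA whose open list already contains three such variables. Carried out as written, the ANCOVA can remove part of the effect the trial is meant to estimate.

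The size is unknown. The range of 2.25 to 1.5 for a true 3.0 depends on an assumed 25% to 50% mediation through one covariate. With no mediation, under the same model, there is no bias. The direction is probably toward no effect if the covariate carries benefit, but this is not guaranteed: if fortification raised NEC and NEC slowed growth, adjusting for NEC would hide a harm. Entry of further variables through the screen is a risk, not a certainty. The change is worth making before analysis but does not threaten the unadjusted comparison.

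**What to change.** In Section 9a:

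1. Remove the search for confounders as a purpose of the between-arm tests.
2. Keep the t, chi-square and Wilcoxon tests as comparisons of post-randomisation feeding, laboratory and clinical outcomes.
3. Describe baseline variables by arm.
4. Close the ANCOVA list in advance to baseline variables already collected, for example gestational age, birth weight and sex.
5. Report feed interruptions, metabolic acidosis and NEC as outcomes. If an analysis adjusting for them is still wanted, label it as a sensitivity analysis and state that it does not estimate the total effect of early fortification.

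The cost is a few sentences. Data collection does not change, and the 25 per group stands as calculated because it rests on the unadjusted t-test.

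### Siblings may be enrolled, but the planned tests treat all 50 infants as independent and no listed field identifies families; under individual randomisation the cost is some lost power, not false positives (minor)

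*Protocol*

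**What the plan says.** - **Eligibility.** Protocol section 5 states: "All neonates admitted to the NICU who have a birth weight of 1000-1500 grams will be eligible for this study". The three exclusions in section 3 concern anomalies, late start of feeds and growth restriction. None mentions multiple birth, and nothing limits enrolment to one infant per mother.
- **Allocation.** Section 8b, item 1: "Subjects will be randomly assigned to one of two groups using blocked randomization to ensure equal allocation throughout enrollment". Blocks are of size 4 and 6. The unit is the subject, and no rule covers siblings.
- **Shared milk.** Mother's Milk Collection, item 4: "All containers of mother's milk collected in one 24 hour span of time will be pooled into a single container".
- **Analysis.** Section 9a names first "a simple two-sided two-sample t-test will be used as a preliminary test for differences in continuous outcomes", and then: "analysis of covariance (ANCOVA) will be used with the main effect of interest being the group effect". The covariates are given as follows: "Covariates that will be adjusted for include gestational age, total number of feed interruptions, incidence of metabolic acidosis, and NEC". There is no family term.
- **Sample size.** Section 9b works from "assuming an alpha level of 0.05, power of 80%, a common standard deviation of 3.64, and a two-sided two-sample t-test" and concludes: "A sample size of 25 per group, for a total of 50 subjects will be needed".
- **Data.** Neither the list under Data Types and Source Records nor the one in section 9c(i) contains a mother, family or plurality field. Both contain date of birth and gestational age. Section 9c also provides for a separate code list and for two years' storage after completion.

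**The concern.** Siblings share gestational age, the uterine environment and, under the milk-lab rule, the same daily pool of mother's milk. Their 28-day growth velocities are likely to be correlated. A t-test or an ordinary ANCOVA computes its standard error as if they were not.

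The direction of the error depends on how siblings fall across the arms. In opposite arms, the shared part of their outcome cancels from the group difference, so the true standard error is smaller than the computed one. The test is then conservative and discards a precise within-family comparison. In the same arm, the shared part adds up, the computed standard error is too small, and the false-positive rate exceeds 5%. The trial has 25 infants per arm and power close to 80%, so it is worth knowing which case applies and how large the effect is.

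**Working it through.** **1. The protocol's own figure.** With SD 3.64, two-sided alpha 0.05 and 80% power, the noncentral t formula gives 74, 53 and 25 per group for differences of 1.69, 2.00 and 3.00. These are the stated values. (The normal approximation gives 73, 52 and 24.) Power at 25 per group for 13.56 − 10.56 = 3.00 is 81.5% for independent infants.

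**2. Inputs the protocol does not give (assumptions).** Share of infants in twin pairs, *s* = 0.20 to 0.40; sibling correlation, ρ = 0.5 to 0.7.

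**3. How often siblings are split.** Take siblings as consecutive entries and blocks of 4 and 6 as equally likely. Ten consecutive positions then hold 3 adjacent pairs inside a block of 4 (opposite with probability 2/3), 5 inside a block of 6 (3/5) and 2 across a boundary (1/2):

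(3 × 2/3 + 5 × 3/5 + 2 × 1/2) / 10 = 6/10 = 60% in opposite arms.

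**4. Type I error of the t-test (large-sample).** The variance of the group difference, relative to independence, is 1 + *s*ρ × (share of pairs in the same arm − share in opposite arms). Type I error is 2 × [1 − Φ(1.96/√variance ratio)].

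| *s*, ρ | Individual: 1 − 0.2*s*ρ | Type I error | Same arm: 1 + *s*ρ | Type I error |
|---|---|---|---|---|
| 0.20, 0.5 | 0.980 | 4.8% | 1.10 | 6.2% |
| 0.40, 0.7 | 0.944 | 4.4% | 1.28 | 8.3% |

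Simulations of 50 infants in blocks of 4 and 6 agree. Under individual randomisation they gave 3.9-4.7% in one set and 4.3-4.8% in another (correlations 0.5 and 0.8). With siblings kept on one arm they gave 6.5-9.4% and 6.0-8.9%.

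**5. Ceiling on the power gain (large-sample, correlation known).** In units of 1/SD², a singleton contributes 0.25 to the information on the group difference, a split pair 0.5/(1 − ρ) and a same-arm pair 0.5/(1 + ρ). The standardised effect is 3/3.64 = 0.824. Independence gives 50 × 0.25 = 12.5, so the t-test's nominal z is 0.824 × √12.5 = 2.91 and its power is Φ[(2.91 − 1.96)/√variance ratio].

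- *s* = 0.20, ρ = 0.5 (40 singletons, 3 split pairs, 2 same-arm): 10 + 3 × 1 + 2 × 0.333 = 13.67; z = 3.05; power 86%, against 83% for the t-test.
- *s* = 0.20, ρ = 0.7: 10 + 3 × 1.667 + 2 × 0.294 = 15.59; z = 3.25; power 90%, against 83%.
- *s* = 0.40, ρ = 0.7 (30 singletons, 6 split, 4 same-arm): 7.5 + 6 × 1.667 + 4 × 0.294 = 18.68; z = 3.56; power 95%, against 84%.

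**6. Achievable gain.** In practice the correlation must be estimated from 5 to 10 pairs, which costs part of that ceiling. Simulation (3,000 runs per cell) of the t-test against a REML random-intercept model with Kenward-Roger degrees of freedom gave:

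| Infants in pairs | Correlation | t-test | Mixed model |
|---|---|---|---|
| 20% | low end of the range | 81% | 81% |
| 30% | 0.5 | 82% | 84% |
| 40% | 0.5 | 82% | 85% |
| 40% | 0.7 | 83% | 92% |

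Without the small-sample correction, the mixed model rejected a true null 7.1-7.6% of the time under individual allocation. The correction is therefore part of the fix.

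**The case against.** The case against acting is substantial.

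- **Validity is not at risk under the natural reading.** Subject-level randomisation keeps the t-test at or just under 5%. This stands.
- **The gain is small over much of the range.** It is about nil at the low end, 2 to 3 points at 30-40% in pairs with correlation 0.5, and large only in the upper corner. This stands too. Each sibling must separately meet the weight band and pass every exclusion, so the number of pairs could be low.
- **The comparison is with the unadjusted t-test.** The planned ANCOVA adjusts for gestational age, which siblings share. That may absorb part of the correlation, so the gain over the ANCOVA may be smaller than shown.
- **The data lists may not be exhaustive.** The two lists differ from each other, and the collection forms are held elsewhere. A family field may therefore exist; all that can be said is that none is listed.
- **A family term could sit in an SAP that is not shown.** That is true of the model. It is less true of the allocation rule, which has to be fixed before siblings are randomised, or of the identifier, which is best collected from the start.

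A reader might infer that, without a family field, the correlation could never be handled. The documents do not support that. A shared date of birth and gestational age would flag likely siblings, and the code list and medical record could confirm them. The route is indirect and time-limited: data are kept for two years, and section 14 has identifiers deleted once no longer needed. But it exists.

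**Conclusion.** The point holds as a minor one. Multiples may enter, allocation has no sibling rule, the named tests assume independence, and no listed field links families.

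Under individual randomisation, and assuming 20-40% of infants in twin pairs with a correlation of 0.5-0.7, the consequence is a slightly conservative t-test (type I error about 4-5%). The power forgone runs from about nil to about 9 points. Both assumed inputs come from outside the protocol, and the size of the loss depends on them.

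A reader might also infer that the trial's false-positive rate is inflated. That would need siblings to be placed on the same arm, where type I error would be about 6-9%. The protocol does not say this is done, and its subject-level wording points the other way. Because it is silent on siblings, it does not rule the practice out either, which is reason enough for one clarifying sentence. Nothing here calls for more infants.

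**What to change.** 1. Add a coded mother identifier to the study database.
2. State in section 8b that siblings are each randomised individually.
3. In section 9a, add a random intercept for mother to the group comparison of the growth outcomes (REML, Kenward-Roger degrees of freedom; PROC MIXED with DDFM=KR in the SAS already planned).
4. Limit that model's covariates to baseline variables such as gestational age. Leave out feed interruptions, metabolic acidosis and NEC: they arise after randomisation and could be affected by fortification, so adjusting for them could distort the group effect.

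The cost is one extra data field and a few sentences, with no additional infants or procedures. The downside is little or no gain if few siblings enrol. If siblings did end up on one arm, the same model would still protect the test: simulated type I error was 5.1-5.7%, against 6.5-9.4% for the t-test.
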